We will target individuals in our healthcare system residing in Philadelphia with a negative baseline screening CT and an upcoming or missed follow-up screening CT. Participants will be divided into receiving clinic + community support vs routine clinic only (control) based on residential location. The intervention group, consisting of individuals residing in West Philadelphia, will receive the option of enrolling in the CSP for obtaining their recommended LDCT. Community members designated as CSP representatives will receive basic training about LCS, transportation vouchers and information regarding other support services. They will also provide feedback to inform an interactive approach to reevaluating the intervention throughout the course of the study. Primary analysis will measure the 12-month follow-up LDCT adherence rate difference between clinic + CSP group vs clinic only group and its association with CSP enrollment. Additional analyses will measure differences in follow-up LDCT utilization before vs after intervention and extent of enrollment in the CSP in the intervention group. Planning and evaluation of our program will be performed using the widely utilized RE-AIM framework with emphasis on measuring reach, effectiveness, and sustainability of our approach.

Hypothesis: A community support program to facilitate lung cancer screening appointments will improve adherence to yearly follow-up screening compared to routine care alone.

Detailed Research Plan

Significance and Rationale:

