Education: CSP representatives will be trained about the basics of lung cancer screening needed to provide support for patients with an upcoming LDCT appointment. Patient-facing LCS material, adapted from ACR and Penn Medicine websites³⁷, will be created to ensure a fifth-grade readability level and sensitivity to local context in collaboration with a PN experienced in patient education and the CSP representatives. To adapt resources for fifth-grade readability, we will utilize an interactive process guided by resources from LUNGevity³⁸ and the Centers for Medicare and Medicaid Services (CMS) health literacy resource toolkit for making written material clear and effective⁴². Readability will be assessed with a commercial web-based suite of tools (readable.com) using a mean score from multiple validated indices ^{39,40,41}. Patient LCS education material would include information on lung cancer, cost and payment options, risks and benefits of screening, radiation exposure, treatment options and smoking cessation.

Transportation: We will utilize the Uber or Lyft transportation vouchers to provide rides to participants from their home location in West Philadelphia to and from the Penn Medicine downtown hospital locations on the day of their LCS study. Transportation vouchers will be created at an upper limit of \$30, which is expected to result in no out of pocket cost for most patients. The mean distance from the patient's residential address to the closest Penn Medicine hospital location is 2 miles and an approximate round trip ride costs \$22. Participants will also be given the option of a CSP representative arranging their transportation if they do not have access to Uber or Lyft transportation software. Based on projections from our preliminary data, allocation would be made to provide transportation support to 450 patients throughout the study period.

The CSP program will be set up to have month-long intervention periods that end with a review process and planning for the next intervention period, utilizing the agile principle of sprint planning⁴³ (Figure 3). This process

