will allow for iterative changes that incorporate feedback from CSP representatives and foster an equitable research partnership. The radiology PN and CSP representatives will meet weekly to discuss day-to-day activities and hurdles and maintain an open line of communication for daily interactions. Time-sensitive issues will trigger consortium meetings separate from the scheduled monthly review meetings. The initial and monthly consortium meetings will be guided by the RE-AIM framework with emphasis on improving the reach, effectiveness, and maintenance of our interventions (Table 1). The meeting following the 6-month intervention period will be focused on future planning. The Mixed Methods Research Lab (MMRL), under the guidance of co-investigator [name], will provide technical support to facilitate and evaluate the equitable inclusion of the various stakeholder perspectives into the study design and interactive changes.

Table 1. Demonstrating the RE-AIM planning and evaluation metrics

RE-AIM components	Question answered	Metric	Future Planning
Reach	How many patients that were offered entry into the community support program engaged with the representative Reasons for non-participation in program.	Number of patients who chose community support / total number of patients who were offered it; demographic and geographic differences of patients reached vs. not reached	Identify potential reasons for patients not choosing community support Identify other possible forms of community support.
Effectiveness	Did addition of community support option lead to increased adherence to follow-up recommendation?	% Of patients who obtained yearly follow- up LDCT in intervention vs control groups % Of patients in intervention group who obtained yearly follow-up LDCT after intervention vs during a similar prior time frame	Identify and compare characteristics of adherent vs non-adherent patients Capture any unintended consequences of community support for LCS Capture additional barriers to LCS adherence
Maintenance (Sustainability)	If the lung cancer screening community support program is effective, how can it be sustained?	Measure actual cost of community support program	Explore options for additional funding including through grants and institutional support Explore institutional return on investment for increased lung cancer screening utilization through community support program

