Specific Aim 2. Measure the impact of the community support program in improving adherence to lung cancer screening follow-up.

A prospective study would be designed to measure the impact of the CSP on a population level by utilizing aggregated neighborhood level data. The database contains information of patients who received baseline LCS with individual level residential address geocoded to determine neighborhood level characteristics (see preliminary data). The West Philadelphia planning district will be chosen as the intervention group because it is within the catchment area of Penn Medicine, has the highest number of LCS patients and is one of the districts noted to have consistent high rates of smoking prevalence and lung cancer mortality. In addition, we have strong community partnerships in the region. The control group would be individuals residing in the adjacent Southwest Philadelphia planning district which has a similar Yost score - a composite index of socioeconomic status⁴¹. Patients will be stratified into those with upcoming or missed appointments with primary analysis focused on patients with upcoming appointments. Informed consent will be provided prior to patient inclusion in the CSP. All activities will be approved by our Institutional Review Board prior to study commencement

We will identify patients residing in West Philadelphia who underwent lung cancer screening in 2020-2022 with a Lung-RADS 1 or 2 result and have an upcoming or missed appointment in our healthcare system downtown hospitals. We will analyze the EHR and RIS data to identify dates of LDCT upcoming appointments over 6 consecutive months with plans for 6 monthly cycles of intervention (Figure 3). A trained radiology PN will contact patients two weeks prior to their upcoming appointment, provide descriptions of the CSP and offer participation. Patients who agree to participate in the CSP would be contacted by a community representative

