1 week and 1 day prior to their appointment to offer support based on their identified needs and the available resources. The CSP representatives will be provided transportation vouchers, educational material and resources for other social support and liaise with the radiology PN to report information from patient encounters including additional needs and patient plans to attend appointments. Patients with missed follow-up appointments who still receive care at Penn Medicine will be contacted by the radiology PN for inclusion in the CSP program. The CSP representative will offer appointment support and collaborate with the radiology PN to offer a rescheduled LDCT appointment to this group of study participants.

Recruitment and Sample: The eligibility criteria for study inclusion are 1) obtained LDCT in 2020-2022 with a Lung-RADS 1 or 2 result 2) upcoming or missed follow-up LDCT 3) residence in the city of Philadelphia. Preliminary data revealed that 1,328 individuals residing in Philadelphia received a LDCT in 2021, 90% of which are Lung-RADS 1 or 2. Assuming the same number of patients receive LCS in 2022 and follow-up LDCT scans are evenly distributed throughout the year, we anticipate that 598 individuals will have an **upcoming LDCT study** in the first 6 months of 2023 of which 167 (28%) in West and 114(19%) in Southwest planning district will be included in our primary analysis. For secondary analysis, patients residing in West Philadelphia (28%) with **missed appointments** (66%) following a Lung-RADS 1 or 2 recommendation on LDCT(90%) in 2020 and 2021 will be included, resulting in an additional 278 patients.

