Evaluation: Evaluation will be guided by the RE-AIM framework with focus on Reach, Effectiveness and Maintenance of our program (Table 1). Primary outcomes of the study include: 1) difference in obtaining the recommended follow-up LDCT screening study in patients with upcoming appointments between the intervention and control group 2) association between participation in the CSP and adherence to follow-up LDCT. An intention-to-treat approach will be used for our primary analysis to measure the effectiveness of the CSP and will be done 2 weeks after completion of the 6-month intervention period. Chi-squared test will be used to measure a difference in adherence to follow-up LDCT between groups. A logistic regression model will be used to determine the association between adherence and utilization of CSP while controlling for demographic, geographic and socioeconomic variables. Secondary outcomes include: 1) difference in follow-up LDCT utilization in the intervention group compared to a similar period prior to implementation of CSP 2) reach of the CSP (what percentage of participants who were offered it engaged with the CSP representative). Evaluation of reach of the CSP would include descriptive analysis to evaluate differences in characteristics

the CSP and those who did not. Secondary analysis will include patients with **upcoming and previously** missed appointments following a negative screening study from 2020-2022. Mcnemar's test will be used to measure a difference in follow-up LDCT utilization after the

intervention compared to a similar

between participants who utilized

Table 2. Deliverables and Timeline (assuming start date of 11/1/2022)			
Deliverable	Target		
	Completion		
IRB Approval	11/30/2022		
Identification of CSP Representatives	11/15/2022		
Establishment of Consortium	11/30/2022		
Development of Support Material: Education, Transportation etc	12/31/2022		
Initiation of the CSP	01/01/2023		
Completion of the CSP	06/30/2023		
Data and Feedback Analysis	07/31/2023		
Manuscript and Presentation Preparation	09/30/2023		
Develop Structure for Future City-wide CSP	10/31/2023		

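### Primary outcome 2 does not define its CSP exposure or say when it is classified; if the model's utilization means actual use, the odds ratio is biased upward even when the CSP does nothing

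*Combined protocol and SAP*

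**What the plan says.** The exposure of primary outcome 2 has several names.

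- **Abstract:** the primary analysis covers the adherence difference and "its association with CSP enrollment".
- **Specific Aim 2, Evaluation, outcome list:** "association between participation in the CSP and adherence to follow-up LDCT".
- **Same paragraph, model sentence:** "A logistic regression model will be used to determine the association between adherence and utilization of CSP". Adjustment is for demographic, geographic and socioeconomic factors.
- **Same paragraph, reach outcome:** "what percentage of participants who were offered it engaged with the CSP representative".
- **Table 1, reach metric:** "Number of patients who chose community support / total number of patients who were offered it".

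The steps of the programme happen at different times.

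- **Two weeks before (Specific Aim 2):** "A trained radiology PN will contact patients two weeks prior to their upcoming appointment, provide descriptions of the CSP and offer participation". Only patients who agree go on to representative contact.
- **One week and one day before (Specific Aim 2):** representatives make contact "1 week and 1 day prior to their appointment to offer support based on their identified needs and the available resources".
- **Scan day (Specific Aim 1, Transportation):** vouchers pay for rides "to and from the Penn Medicine downtown hospital locations on the day of their LCS study".

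No passage defines utilization, says when a patient is classed as a user, or says whether Southwest patients enter this model. The Evaluation paragraph names intention-to-treat for the primary analysis. Power Considerations covers only the comparison of adherence between districts.

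**The concern.** An exposure should be fixed before the outcome can influence it. The only sentence that specifies the model names utilization, and an analyst could reasonably build that variable from ride or contact records.

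Ride use strictly depends on travelling to the scan. Contact comes before the scan, but a patient who cancels or withdraws between the two-week call and the one-week contact may never be counted as a user and will often be non-adherent. In both cases non-attenders are moved into the unexposed group, and the odds ratio rises above 1 without any benefit from the programme.

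This is separate from volunteer bias, because it arises even if acceptance is a coin toss. The planned covariates do not capture cancellation or intention to attend, so they cannot remove it. What is at stake is one of the two primary outcomes. Leaving the definition open also allows it to be chosen once outcomes are known.

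**Working it through.** **The plan's own figure.** No power or effect size is given for the logistic model. The stated figure belongs to primary outcome 1: N = 281 (167 West, 114 Southwest), W = 0.17, 1 df, two-sided 5%. The noncentrality is 281 × 0.17² = 8.12 and power is 81.3%. The smallest W with 80% power is 2.80/√281 = 0.167, which rounds to 0.17. The figure reproduces, and the exposure definition does not affect it.

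**Inputs for primary outcome 2.** From the documents: 167 West and 114 Southwest patients, and 24% baseline adherence after Lung-RADS 1 or 2 (Preliminary Data). Assumed, because the documents give no values: share agreeing at the call e = 50%, independent of attendance; share q of eventual non-attenders who drop out before the one-week contact; no CSP effect.

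**Reading A: use means agreement at the two-week call.** The user share is e among attenders and non-attenders alike, so OR = 1.00.

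**Reading B: use means representative contact.** The user share is e among attenders and e(1 − q) among non-attenders:

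OR = odds(e) / odds(e(1 − q)), where odds(x) = x/(1 − x).

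For q = 20%: odds(0.50) = 1, odds(0.40) = 0.667, OR = 1.50.

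If the Southwest patients are pooled as non-users, e is replaced by (167/281) × 0.50 = 0.297. For q = 20%: odds(0.297) = 0.423, odds(0.238) = 0.312, OR = 1.36.

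The rejection rates below are for a conclusion in favour of the CSP (nominal 2.5%), from 40,000 simulated trials at 24% adherence with an unadjusted Wald test and 0.5 added to each cell.

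| q | OR, West only | Rejection, West only | OR, pooled | Rejection, pooled |
|---|---|---|---|---|
| 0% | 1.00 | 2.4% | 1.00 | 2.5% |
| 5% | 1.11 | 4% | 1.07 | 5% |
| 20% | 1.50 | 20% | 1.36 | 17% |
| 40% | 2.33 | 63% | 1.95 | 55% |

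The closed-form odds ratios do not depend on the adherence rate.

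**Reading C: use means a ride taken to the scan.** At 24% adherence, suppose a share r of agreeing attenders takes the ride (assumed). Users are 0.24 × 0.5 × r of West patients, essentially all adherent. Adherence in all other West patients is:

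- r = 50%: (0.24 − 0.06)/(1 − 0.06) = 19%
- r = 80%: (0.24 − 0.096)/(1 − 0.096) = 16%

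The cell for used and not adherent is empty, while non-users include both adherent and non-adherent patients. This is quasi-complete separation, and the maximum-likelihood odds ratio is not finite.

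**What fixing the exposure at the call leaves behind.** Suppose 30% of patients intend to attend and 50% of them do. Overall adherence of 24% then needs (0.24 − 0.15)/0.70 = 12.9% among the rest. If intenders agree 60% of the time and others 40%:

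- Adherence in agreers: (0.3×0.6×0.5 + 0.7×0.4×0.129)/(0.18 + 0.28) = 27.4%
- Adherence in decliners: (0.3×0.4×0.5 + 0.7×0.6×0.129)/(0.12 + 0.42) = 21.1%
- OR = 1.41 with no CSP effect

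With 60% of intenders attending and agreement of 70% against 30%, OR = 2.63. All these inputs are assumed. They show that self-selection survives the repair.

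**The case against.** The strongest reply is that the plan may already mean agreement at the call. The outcome is worded as participation, participation is what the navigator offers two weeks ahead, consent precedes inclusion, and Table 1 counts patients who chose support. On that reading the timing bias is zero. This stands, and it is why the point is conditional. It does not settle the matter, because the model sentence says utilization and the reach outcome is described as engagement with the representative.

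A reader might infer more than the documents support, in four ways:

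- **That the inflation is certain.** It depends on which meaning of an undefined word is applied.
- **That contact is set after the outcome.** It precedes the scan. The link runs through earlier cancellation or withdrawal, and only ride use strictly follows attending. The documents do not say that contact stops after a cancellation, and a rescheduled scan might still count as adherent.
- **That the ride is the main service, so the estimate must break down.** The plan lists education alongside transportation, with other support possible. A patient who received education and stayed away would be a non-adherent user. The estimate fails to exist only if rides alone count.
- **That the programme's effectiveness claim falls.** The Evaluation paragraph ties effectiveness to the intention-to-treat analysis, Table 1 measures it by district and before-after contrasts, and outcome 2 is called an association.

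It is also fair to object that the drop-out and acceptance values have no source in the documents. At q = 5% the bias is small, and at q = 0 it vanishes.

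**Conclusion.** The point holds in conditional form. The exposure of primary outcome 2 carries different names, with no definition and no classification time. If it is counted from actual use, the odds ratio is biased upward with no CSP effect and random acceptance, and the planned covariates do not correct this.

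The size cannot be derived from the documents. With 50% acceptance and 0% to 40% early drop-out among non-attenders (both assumed), the West-only odds ratio runs from 1.00 to 2.33, and the pooled one from 1.00 to 1.95. A ride-only definition gives no finite estimate. If the exposure is agreement at the two-week call, this bias is absent, although self-selection is not.

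This is more than a wording matter, because applying the model sentence literally can give a misleading primary result. Primary outcome 1 and its stated power are unaffected.

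**What to change.** 1. In the Abstract and the Evaluation paragraph, use one exposure: agreement to CSP participation (yes/no) at the navigator's call two weeks before the appointment, fixed at that call and never updated.
2. Report representative contact and ride use descriptively only, and do not enter them as predictors of adherence.
3. State whether Southwest patients enter the logistic model and, if so, how they are coded.
4. Label the result a non-causal association, because patients who agree may already be more likely to attend.
5. Rest the conclusion on effectiveness on the intention-to-treat comparison between districts.

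The cost is a few sentences in the analysis plan. No further patients are needed, and agreement has to be recorded anyway for the reach measure in Table 1. The downside is that the reported association will probably be smaller.
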